RESEARCH PROTOCOL

Study identification data

Study Title

Conservative approach to dysfunctional pain in women

Study version number and date

V.01 (01-12-2021)

Promoter and direction

[name]. [name]

Principal Investigator and Director

[name]. [name]

Service or Unit

Gynecology/Rehabilitation

Centers where the study is planned (multicenter studies)

Hospitals of Sagunto, La Plana, IMSKE Valencia and University of Valencia

Study Summary

Study that will seek to compare the effects of the implementation of a therapeutic education program in women suffering from dyspareunia for a period of more than three months who do not have any previous medical condition that can logically explain this condition. The effects of three groups will be compared; one that attends face-to-face workshops, another that will receive access to a website where the educational content will be, and a third that will serve as control.

Study Introduction

This research project is entitled "Conservative approach to the patient with dysfunctional pain in the pelvic floor in women". It will be carried out both by researchers from the University of Valencia and by external researchers from other hospitals.

Conservative approach to dysfunctional pain in women

We understand dysfunctional pain as pain that stops fulfilling the function of "alarm signal" and that stops responding to a nociceptive stimulus (1). This alarm signal can be triggered by previous pathologies, such as endometriosis (2) or musculoskeletal conditions such as muscle hypertonia (3) or neuralgia (4).

Despite this, this pain can also originate without the existence of any of the previous conditions, therefore without having a clear origin that can be addressed through treatment. In the pelvic floor, this dysfunctional pain can come to take different names, among which we highlight "dyspareunia" and "vestibulodynia" (5).

"Dyspareunia" is a term derived from the Greek that means lovers who do not fit together (6), and it is a sexual disorder that is defined by the presence of pain and discomfort during the sexual act, in addition to being predominantly associated with the attempt or achievement of sexual intercourse. complete vaginal penetration (7). Prevalence levels range from 3% to 43%, and vary depending on different cultures and settings (6) (8).

Study justification

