The lack of a good educational level in women's health disorders can lead to misinterpretations about normality, and these end up causing both sexual and emotional repercussions (8). It is a common misconception that intercourse can sometimes be painful, and many women are forced to continue intercourse even in pain, even having to clench their teeth.

Because of this, women who suffer from dysfunctional pelvic floor pain develop clinically relevant comorbidities, especially psychological ones, such as depression, anxiety or erotophobia (6) (8) .

Conservative approach to dysfunctional pain in women

For this reason, the treatment of dysfunctional pain with therapeutic educational sessions is proposed so that women who suffer from dyspareunia are able to better understand the processes of this condition and, possibly, solve it.

Study Objectives

The main objective of this study is to compare the effects of implementing a therapeutic educational program on pelvic floor pain and dysfunction in patients with dysfunctional pain. This program will be administered both in person at workshops organized in different centers, and online through a web platform.

As a secondary objective, the adherence levels of each of the proposed educational programs will be analyzed.

Material and methods

Design

Randomized controlled clinical trial.

Disease or Study population and total number of subjects

Women with dysfunctional pelvic floor pain that cannot be explained by another underlying medical cause

Selection criteria (inclusion and exclusion)

Women who (1) are of legal age, (2) have suffered from dyspareunia for more than 3 months and (3) do not have any medical condition that logically explains the presence of pain

Main variables

Level or intensity of pain, evaluated using subjective perception scales (Visual Analogue Scale or VAS).

Conservative approach to dysfunctional pain in women

Secondary variables

Other questionnaires related to dysfunctional pain; Pain Catastrophizing Scale to quantify the patient's individual experience of pain, the Multidimensional Pain Inventory to measure the impact of pain on the patient's life, the Survey of Pain Attitudes related to the patient's beliefs about pain, and the Female Sexual Function Index related to the patient's sexual function.

The levels of adherence to the different programs will also be evaluated, established by the percentage of sessions completed based on the total number of sessions offered.

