Regarding the control group, initially the participants of this group will not receive any of the two previous interventions, this group will serve to establish how the condition is maintained without a therapeutic approach. Once the intervention has finished and the post measurements have been collected, the participants of this group will also be given access to the online study so that they can view the contents and comment through the forum.

Work calendar

Calendar	Exercise	Place	Responsible
October to December 2021	Subject Selection	H. La Plana, H. IMSKE, H. Sagunto, University of Valencia	[name], [name], [name]
December 2021 to January 2022	Measurements prior to the start	H. La Plana, H. IMSKE, H. Sagunto,	[name], [name]

Conservative approach to dysfunctional pain in women

	of the intervention	University of Valencia	[name], [name]
January to March 2022	Intervention. Educational sessions on dysfunctional pain	H. La Plana, H. IMSKE, H. Sagunto, University of Valencia and online modality	[name], [name], [name]
March to April 2022	Post-intervention measurements	H. La Plana, H. IMSKE, H. Sagunto, University of Valencia and online modality	[name], [name], [name]
April 2022	Preparation of a scientific article with the results obtained from the research		[name]

Statistical analysis of data: equal to or less than 0.05)

The study design aims to collect pre and post measurements with various interventions. To do this, since these are pre and post measurements with several groups, a factorial ANOVA will be carried out, a repeated measurement factor (time) and a factor between groups (intervention).

The changes that are intended to be achieved are, with respect to the main variable, a significant reduction in the values of the VAS scale that corresponds to an improvement in terms of pain intensity. Regarding the secondary variables, significant changes in the score of the questionnaires on dysfunctional pain and sexual function that indicate clinical improvements regarding the impact of pain on the life

Conservative approach to dysfunctional pain in women

of the participant and the beliefs about the pain of the same, and on the levels of adherence, find high values to be able to relate the results obtained with the implementation of the program.

Sample size calculation and sampling procedure

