The sample size was determined using the G-Power computer program. An a priori size calculation was performed with an effect power of 80% and an alpha error of 0.05. It was determined that the sample must have a minimum of 48 participants, and that each group must have a minimum of 16. Taking into account possible drop-outs, it was determined that a minimum sample of 60 participants and 20 participants for each group.

Ethical aspects and data confidentiality

This research deals with the implementation of an educational program on dysfunctional pelvic floor pain in women. It does not involve an invasive or aggressive intervention that could cause negative effects on the participants. In addition, if the final result is positive, there will be a tool that is easy to implement daily for the treatment of patients with this problem.

Conservative approach to dysfunctional pain in women

The subjects will be informed at all times of how the research will proceed, and before being included in the study sample they will be required to give their consent, both verbal and written, to participate in this research.

We will ensure that the data provided by patients is strictly confidential. Patients will be coded to ensure their anonymity and both the principal investigator and the person in charge of processing the statistical data will be blinded to the group assignment and to which patient corresponds to which value.

During the development of the investigation there will be no interference with regard to medical action. Once the study is over, and if the result is positive, the medical staff will be provided with the material with which the research has been carried out so that they can use it in their daily practice.

Sources of funding

The study has sufficient material and human resources to carry it out. Two researchers will coordinate its development, and the rest of the researchers will be in charge of carrying out the measurements prior to the start of the intervention, implementing the educational program and finally performing the measurements again. No medication will be supplied and there is no need for funding to carry out this research.

Bibliography

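### Does the missing effect size behind the 48-participant calculation call for a change to the plan?

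*Combined protocol and SAP*

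**What the plan says.** Under Sample size calculation and sampling procedure, the protocol names the software and states: "An a priori size calculation was performed with an effect power of 80% and an alpha error of 0.05". It continues: "It was determined that the sample must have a minimum of 48 participants, and that each group must have a minimum of 16". An allowance for drop-outs brings the target to 60, or 20 per arm. The section does not give the G-Power test, the effect size, an SD, a pre-post correlation or a drop-out rate, and no other section supplies them.

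The rest of the protocol shows what the trial is for. The Study Summary says "The effects of three groups will be compared", and the Study Objectives say "The main objective of this study is to compare the effects of implementing a therapeutic educational program on pelvic floor pain". On the control arm, the interventions section says "this group will serve to establish how the condition is maintained without a therapeutic approach". The main variable is pain intensity on the VAS, and the statistical section says "a factorial ANOVA will be carried out, a repeated measurement factor (time) and a factor between groups (intervention"). The aim for the VAS is worded as "a significant reduction in the values of the VAS scale that corresponds to an improvement in terms of pain intensity", with no size and no comparator.

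**The concern.** A sample size is normally tied to a named test and a stated difference. Here neither is given. A two-way ANOVA with time and group factors has three F tests, and they differ greatly in what 48 participants can detect. The main effect of time reaches 80% power at an average change of only 0.41 SD of change, but it does not compare arms. The group-by-time interaction, which does compare them, needs about 1 SD. Because the VAS aim is worded as a reduction without a comparator, a reader could suspect that the 80% belongs to the easier test.

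At stake is how a null result would be read. If education beat control by 0.5 SD of change, the interaction test with 48 completers would miss it about 73% of the time. With no stated target, the protocol alone would not tell a reader whether the trial had been sized for such a benefit.

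**Working it through.** **Inputs from the protocol:** power 80%, alpha 0.05, three arms, two measurements, 48 completers (16 per arm), 60 enrolled (20 per arm). **Inputs not in the protocol:** effect size, SD and pre-post correlation (rho). Any value used for these below is an assumption.

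**Can 48 be reproduced?** Not uniquely. For the interaction in a repeated-measures ANOVA with two time points, the noncentrality is lambda = N × f² × 2/(1 − rho), on 2 and N − 3 degrees of freedom. Searching in multiples of three, 48 is the smallest N reaching 80% for:

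- f = 0.20 with rho 0.63 to 0.65
- f = 0.25 with rho 0.42 to 0.45
- f = 0.30 with rho 0.17 to 0.21

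With f = 0.25 and rho = 0.5 the answer is 42, and power at 48 is 86%. The time main effect gives 48 at f = 0.25, rho = 0.3. The group main effect gives 48 at f = 0.40, rho = 0.4. So 48 is attainable for the between-arm test with unremarkable inputs, but it does not identify them. The step to 60 fits an unstated 20% loss: 48/(1 − 0.20) = 60.

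**What 48 completers deliver.** With two time points the interaction is a one-way F test on change, with 2 and 45 degrees of freedom. Put d in SDs of change. Then lambda = 16 × Σ(d_g − mean d)², and 80% power needs lambda = 10.306.

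- Both education arms (or only one) differ from the rest by d: the sum is 2d²/3, so d = √(10.306 × 3/32) = 0.98.
- Arms evenly spaced, with D between the extremes: the sum is D²/2, so D = √(10.306/8) = 1.14.

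These two results need no assumed SD or rho.

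| True d (SD of change, first pattern) | Power, 48 completers | Completers for 80% |
|---|---|---|
| 0.5 | 27% | 177 |
| 0.7 | 49% | 93 |
| 0.8 | 61% | 72 |

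**How far the 0.98 figure extends.** It applies to the unadjusted test with exactly 48 completers.

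- If all 60 complete, lambda = 10.160 with 20 per arm, so d = √(10.160 × 3/40) = 0.87, or D = √(10.160/10) = 1.01 if evenly spaced. Power at d = 0.8 is then 72%.
- A baseline-adjusted comparison with 48 completers needs 0.94, 0.85 or 0.70 raw SD at assumed rho of 0.3, 0.5 or 0.7. Dividing by √(2(1 − rho)) gives 0.79, 0.85 or 0.91 SD of change.
- The difference that gives 80% power is not the smallest that can reach significance. The critical F(2,45) is 3.204. For the first pattern F = 16 × (2d²/3)/2 = 16d²/3, so an observed d of √(3.204 × 3/16) = 0.78 SD already gives p = 0.05.

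**The case for a change.** The strongest case for acting is that the test name can be supplied later but a target difference cannot, because one chosen after the data are seen carries no weight. A conventional input does not rescue the plan either: on the raw scale d = f/(0.5 × √(2/9)), so f = 0.25 already means both education arms beat control by 0.25/0.2357 = 1.06 raw SD, a large effect for an educational programme. Reporting the inputs would cost a paragraph.

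Part of this stands. The effect size is missing, it cannot be inferred, and the detectable difference is large on every reading. Anyone citing the 80% should know that.

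Three things limit it. First, the protocol calls the calculation a priori, so the inputs should already exist with the sponsor; setting them out is reporting, not a new decision. Second, the test is not really in doubt: three arms to be compared, an untreated control and a time-by-group ANOVA point to the interaction, and an analyst would use it. Third, a null result is not unreadable. A confidence interval for the difference from control can be set against whatever VAS difference a reader regards as worthwhile, whether or not the protocol named one. The 73% miss rate rests on a 0.5 SD benefit that the protocol nowhere expects or calls worthwhile.

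The larger remedy is expensive. Sizing for 0.7 SD means 93 completers, which at the protocol's own ratio of 60 to 48 is 93 × 60/48 ≈ 117 enrolled, almost double the planned 60, with subject selection scheduled for October to December 2021.

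**Conclusion.** The omission is confirmed, but it does not show that 48 is wrong or that the trial is too small for its aim. For the unadjusted group-by-time test with 48 completers, 80% power needs at least 0.98 SD of VAS change between the extreme arms (1.14 SD if evenly spaced). With all 60 completing it needs 0.87 to 1.01 SD, and a baseline-adjusted test at 48 needs about 0.79 to 0.91 SD of change for assumed rho of 0.3 to 0.7. All of these assume equal arms, which simple randomization does not guarantee; imbalance would raise them slightly.

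This is a gap in reporting that competent analysts fill in the usual way: they take the interaction as the between-arm test, give the G-Power inputs with the results, and present between-arm differences with confidence intervals. No stated figure needs correcting, and neither the planned ANOVA nor the target of 60 needs to change on this ground.

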Interventions/procedures to be performed

Initial phase of patient recruitment from various hospital centers and by broadcasting with an informative video on RRSS through the official profiles on Instagram, Facebook and Twitter of the University of Valencia and the Illustrious College of Physiotherapists of the Valencian Community. The hospital centers that will initially be considered for obtaining the sample are the La Plana and Sagunto Hospitals and the IMSKE Hospital in Valencia. After this first phase, and using the established inclusion and exclusion criteria, randomization of all the participants into three different groups. The randomization method will be a simple randomization performed through computer software.

One group (1) will receive a therapeutic education program on pelvic floor pain and dysfunction in person as workshops held at collaborating centers, a second group (2) will receive access to a web platform where they can view as online content this same educational program and a third group (3) that will serve as control.

Conservative approach to dysfunctional pain in women

Both group (1) and group (2) will receive the same educational content, the only thing that will change is the modality in which they can access it, face-to-face through workshops given by specialist trainers, or access to an online platform where the contents previously recorded by these same trainers will be.

a "forum" will be opened on the same website where they can comment on their doubts). Each workshop will last approximately one hour, and the schedule will be established according to the possibilities of the participants.

The web platform will be developed thanks to a researcher who already has an online studio where she teaches therapeutic exercise classes, available at <[name]>. Participants who have been randomized in the online group will be given an access code to be able to enter the online space where they will have both the audiovisual material that has been previously developed by the researchers and a forum where they can discuss their doubts.

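### The only named VAS analysis, a pre/post time-by-group ANOVA, is in effect a test on change scores: less precise than a baseline-adjusted comparison, open to bias from baseline-related loss, and by default without women who lack a post VAS

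*Combined protocol and SAP*

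**What the plan says.** Under *Statistical analysis of data* the plan describes pre and post measurements in several groups and names one method: "a factorial ANOVA will be carried out, a repeated measurement factor (time) and a factor between groups (intervention". The aim for the main variable is "a significant reduction in the values of the VAS scale that corresponds to an improvement in terms of pain intensity". No other model is named and no baseline adjustment is mentioned. The heading of that section is damaged in the available text ("Statistical analysis of data: equal to or less than 0.05"), and a paragraph about the forum under *Interventions/procedures to be performed* starts in mid-sentence. A lost sentence therefore cannot be excluded.

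Under *Sample size calculation and sampling procedure* the minimum is 48 women, 16 per group, and then: "Taking into account possible drop-outs, it was determined that a minimum sample of 60 participants and 20 participants for each group". No drop-out rate is given. Under *Secondary variables* adherence is "established by the percentage of sessions completed based on the total number of sessions offered", so partial attendance is foreseen.

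The *Work calendar* puts the post measurements in March to April 2022, at "H. La Plana, H. IMSKE, H. Sagunto, University of Valencia and online modality". The available text has no sentence on whether a woman who stops the programme is still asked for her post VAS, on the analysis set, or on missing values.

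**The concern.** Three consequences follow from relying on change scores.

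1. **Precision.** A change score subtracts the whole baseline value, although baseline predicts only part of the post value. Unless the pre-post correlation is close to 1, this adds noise that baseline adjustment avoids. In a trial of 48 to 60 women that is a real loss.
2. **Loss related to baseline.** If women with more baseline pain are more likely to leave one arm, the remaining women differ in expected change and the contrast is biased. Baseline adjustment removes this.
3. **Loss related to the outcome.** A woman without a post VAS has no change score. If the women lost from one arm did worse or better than those who stayed, and this differs between arms, the comparison of completers is no longer the randomised comparison. The bias can go either way, and no choice of model removes it.

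The arms ask different things of women: scheduled workshops, self-directed web access, or no programme until after the post measurement. Unequal loss is therefore possible, but loss by arm is not known.

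**Working it through.** **Plan's own figures.** Inputs from the sample size section: 48 and 60 in total, 16 and 20 per group. 48/0.80 = 60 and 16/0.80 = 20, so the allowance fits 20% loss: (60 − 48)/60 = 12/60 = 20%. The 20% is back-calculated. The 48 itself cannot be reproduced, because effect size, SD, correlation and test family are not stated.

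**Equivalence.** With two time points, the time-by-group F equals the one-way ANOVA F on post minus pre. On a simulated set of 3 × 20 women both were 8.360.

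**Precision.** Units are SD of VAS, with 16 women per arm and r assumed, because the documents give no correlation.
- Change scores: SE = √(4(1−r)/16)
- Baseline-adjusted: SE = √(2(1−r²)/16)
- Variance ratio: 2(1−r²) / 4(1−r) = (1+r)/2

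| r (assumed) | SE, ANOVA | SE, adjusted | Variance ratio |
|---|---|---|---|
| 0.3 | 0.418 | 0.337 | 0.65 |
| 0.5 | 0.354 | 0.306 | 0.75 |
| 0.7 | 0.274 | 0.252 | 0.85 |

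At r = 0.5, 48 women analysed with adjustment are worth about 48/0.75 = 64 analysed by the ANOVA. The formula ignores the small cost of estimating one slope, so it is slightly favourable at this sample size.

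**Loss related to baseline.** Benefit is a fall in VAS; positive bias overstates the benefit of education. The bias of the change-score contrast is p₁d₁ − p₀d₀ (1 = education, 0 = control), where p is the loss fraction and d is how much less leavers improve than completers. Assumed example: true effect 1 SD, 20% loss per arm, loss rising with baseline pain in education only (odds ratio 2.2 per SD). Leavers start 0.72 SD worse, so they improve 0.72(1−r) more and d = −0.72(1−r).
- r = 0.3: 0.20 × (−0.50) = −0.10
- r = 0.5: 0.20 × (−0.36) = −0.07
- r = 0.7: 0.20 × (−0.22) = −0.04

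Simulation with 1,000,000 per arm agrees: at r = 0.5 the ANOVA gives 0.93 and the adjusted model 1.00 against a truth of 1.00. With the same pattern in control only, the ANOVA gives 1.07 and the adjusted model 1.00.

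**Loss related to the unseen post value.** Suppose education leavers do not improve and loss is unrelated to baseline, so d = 1.00 in education and 0 in control. The bias is 0.20 × 1.00 = +0.20 SD. Truth is 0.80, and ANOVA and adjusted model both give 1.00. The bias is 0.20/0.354 = 0.57 of one ANOVA SE.

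Rejection by the planned F test with no true effect (20 randomised per arm, r = 0.5, 20% loss, 200,000 runs):

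| Assumed gap | Bias (SD), education against control | Rejection |
|---|---|---|
| None | 0 | 5.0% |
| 1 SD, equal loss in all arms | 0 | 5.0% |
| 0.5 SD, both education arms only | 0.10 | 5.7% |
| 1 SD, both education arms only | 0.20 | about 8% |

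If a fraction f of leavers is retrieved and they are typical of leavers, the residual bias is pd − pfd/(1−p+pf). With p = 0.20 and d = 1:
- f = 0.5: 0.20 − 0.10/0.90 = 0.09
- f = 0.75: 0.20 − 0.15/0.95 = 0.04
- f = 1: 0.20 − 0.20/1.00 = 0

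**Dilution.** If 48 completers give 80% power under the ANOVA (r = 0.5), 60 analysed women give 88.9% for the same effect. If including women who stopped shrinks the effect to 0.8 of its size, power with 60 is about 71% under the ANOVA and about 83% with adjustment.

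**The case against.** A reader might infer that the plan has a rule dropping women without a post VAS, or that it intends to analyse attenders only. The documents support neither. Omission follows from a classical repeated-measures ANOVA without imputation; it is not a written rule. The only groups defined are the three randomised ones, there is no completion threshold or per-protocol set, and post measurement carries no attendance condition. Controls get access only after the post measurements, so the plan has no crossover before the endpoint. An explicit sentence would help, but its absence alone is missing detail, at a point where the text is damaged.

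A reader might also take 8% as this trial's false-positive rate. It is not: it needs an assumed 1 SD gap confined to some arms. With gaps of 1, 1 and 0.5 SD, rejection is about 5.5%; with 10% loss and a 1 SD gap in the education arms only, about 5.8%. Twenty per cent is an allowance for possible drop-outs, not a forecast. Flexible scheduling ("the schedule will be established according to the possibilities of the participants") and later access for controls may help retention.

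Blinding counts as well: "both the principal investigator and the person in charge of processing the statistical data will be blinded to the group assignment". It limits an analysis choice made to favour one arm, but it neither recovers missing values nor improves precision.

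Finally, changing the model does not cure outcome-related loss. That stands. The case for adjustment rests on precision and on baseline-related loss, and the precision gain is there even if nobody drops out.

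**Conclusion.** The point holds as a concrete improvement in the primary analysis that uses data already collected. The change-score ANOVA gives away precision: adjustment cuts the contrast variance by (1−r)/2, or 25% at r = 0.5 (35% at 0.3, 15% at 0.7). It is also biased when loss depends on baseline pain, by 0.04 to 0.10 SD in the assumed example. The variance result needs only an assumed r; the bias figures need an assumed loss pattern as well.

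The effect of outcome-related loss is not known from the documents. The 0.20 SD and 8% are illustrations, falling to 0.10 SD and 5.7% with a 0.5 SD gap and to 0 and 5% when loss and gap are equal across arms. The sample size of 60 is not shown to be wrong. The plan should make the change; confidence is medium, because the analysis section is damaged.

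**What to change.** **Main change.** For VAS, replace the factorial ANOVA with a baseline-adjusted comparison of women in the group to which they were randomised. Either use ANCOVA of post VAS on group and baseline VAS, or the equivalent likelihood model with baseline and post VAS as outcomes, a common baseline mean and group-by-time. ANCOVA still cannot use a woman without a post value; the likelihood model keeps her baseline. Neither corrects loss related to the unseen post value.

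**Supporting step.** In the existing March to April window, ask every randomised woman who has not withdrawn consent for the post VAS, whatever her attendance. Report loss by arm.

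**Cost.** One paragraph in the plan, a little analysis work and contact effort for up to about 12 women. The online modality in the post-measurement row might avoid extra visits, but the same words stand in the intervention row and may refer only to the online arm, so this needs confirming. Including women who stopped may dilute the effect; the power figures above show the possible price and how far adjustment offsets it.
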